7.7.5.2. Management of Increased Hypoglycemia Risk

If a hypoglycemic event occurs, the patient should record in the study diary the BG level measured during the episode and prior to administration of treatment (if taken), as well as associated symptoms and treatment administered. Site personnel will enter this information into the hypoglycemia eCRF at each visit. ~~Patients should be instructed to call the investigative site as soon as possible if they experience a hypoglycemic event that requires assistance to administer treatment. Patients should be trained about signs and symptoms of hypoglycemia and how to manage hypoglycemia. Patients should first seek acute medical or emergency care if needed, and inform the investigative site as soon as possible after an event of severe hypoglycemia has occurred that requires assistance to administer corrective treatment.~~

In this study, increased risk of hypoglycemia is defined as having a single episode of severe hypoglycemia or having more than 1 episode of documented symptomatic hypoglycemia (≤ 3.0 mmol/L) within a 1-week period at any time during the Treatment Period.

8.1.1. Permanent Discontinuation from Study Treatment

- Any significant study drug-related hypersensitivity reaction;
- ~~If a patient requires a new intervention due to severe, persistent hyperglycemia;~~
- If a non-study GLP-1 receptor agonist is initiated, and the patient refuses to discontinue this medication;

9.2.2.1. Hypoglycemia

Investigators should use the following definitions and criteria when diagnosing and categorizing an episode considered to be related to hypoglycemia (the BG values in this section refer to values determined by a laboratory or International Federation of Clinical Chemistry and Laboratory Medicine plasma-equivalent glucose meters and strips) in accordance with the 2017-2020 ADA position statement on glycemic targets:

Level 1 hypoglycemia:

Glucose <70 mg/dL (3.9 mmol/L) and ≥ 54 mg/dL (3.0 mmol/L): Level 1 hypoglycemia can alert a person to take action such as treatment with fast-acting carbohydrates. Providers should continue to counsel participants to treat hypoglycemia at this glucose alert value.

Level 2 hypoglycemia:

Glucose <54 mg/dL (3.0 mmol/L): This is also referred to as documented or blood glucose confirmed hypoglycemia with glucose <54 mg/dL (3.0 mmol/L). This glucose threshold is clinically relevant regardless of the presence of absence of symptoms of hypoglycemia.

Level 3 hypoglycemia:

Severe hypoglycemia (in adults): A severe event characterized by altered mental and/or physical status requiring assistance for treatment of hypoglycemia. For example, participants had altered mental status, and could not assist in their own care, or were semiconscious or unconscious, or experienced coma with or without seizures, and the assistance of another person was needed to actively administer carbohydrate, glucagon, or other resuscitative actions. Glucose measurements may not be available during such an event, but neurological recovery attributable to the restoration of glucose concentration to normal is considered sufficient evidence that the event was induced by a low glucose concentration.

- The determination of a hypoglycemic event as an episode of severe hypoglycemia, as defined above, is made by the investigator based on the medical need of the participant to have required assistance and is not predicated on the report of a participant simply having received assistance.
- If a hypoglycemic event meets the criteria of severe hypoglycemia, the investigator must record the event as serious on the AE CRF and report it to Lilly as an SAE.

Nocturnal hypoglycemia:

Nocturnal hypoglycemia is a hypoglycemia event (including severe hypoglycemia) that occurs at night and presumably during sleep.

Glucose Alert Value (Level 1):

- **Documented symptomatic hypoglycemia** is defined as any time a patient feels that he/she is experiencing symptoms and/or signs associated with hypoglycemia, and has a BG level of $\leq 3.9 \text{ mmol/L}$.
- **Documented asymptomatic hypoglycemia** is defined as any event not accompanied by typical symptoms of hypoglycemia, but with a measured BG $\leq 3.9 \text{ mmol/L}$.
- **Documented unspecified hypoglycemia** is defined as any event with no information about symptoms of hypoglycemia available, but with a measured BG $\leq 3.9 \text{ mmol/L}$.

Clinically Significant Hypoglycemia (Level 2):

- **Documented symptomatic hypoglycemia** is defined as any time a patient feels that he/she is experiencing symptoms and/or signs associated with hypoglycemia, and has a BG level of $< 3.0 \text{ mmol/L}$.
- **Documented asymptomatic hypoglycemia** is defined as any event not accompanied by typical symptoms of hypoglycemia, but with a measured BG $< 3.0 \text{ mmol/L}$.

- ~~Documented unspecified hypoglycemia is defined as any event with no information about symptoms of hypoglycemia available, but with a measured BG < 3.0 mmol/L.~~

Severe hypoglycemia (Level 3):

- ~~Severe hypoglycemia is defined as an episode with severe cognitive impairment, requiring the assistance of another person to actively administer carbohydrate, glucagon, or other resuscitative actions. These episodes may be associated with sufficient neuroglycopenia to induce seizure or coma. Blood glucose measurements may not be available during such an event, but neurological recovery attributable to the restoration of BG to normal is considered sufficient evidence that the event was induced by a low BG concentration.~~

Other hypoglycemia categories:

- ~~Nocturnal hypoglycemia is defined as any hypoglycemic event that occurs between bedtime and waking.~~
- ~~Relative hypoglycemia is defined as any symptomatic event during which the person reports any of the typical symptoms of hypoglycemia and interprets those as indicative of hypoglycemia, but a measured BG concentration > 3.9 mmol/L is collected.~~
- ~~Probable symptomatic hypoglycemia is defined as symptoms of hypoglycemia but BG measurement was not reported.~~

~~All reported cases of hypoglycemia will be reported on the hypoglycemia eCRF. If a hypoglycemic event meets the criteria of severe, it also needs to be recorded on the AE eCRF as serious and reported to Lilly as an SAE.~~

To avoid duplicate reporting, all consecutive BG values ≤ 3.9 mmol/L occurring within a 1-hour period may be considered to be a single hypoglycemic event (Weinberg et al. 2010; Danne et al. 2013, ADA 2020).

9.2.2.5. Cardiovascular Events

~~Vital signs (PR, SBP, DBP) will be monitored throughout the study, and 12-lead electrocardiograms (ECGs) will be monitored at screening and Visit 17 (Week 28). Any clinically relevant finding from vital signs and ECGs obtained before the first dosing of study drug that results in a diagnosis should be recorded in eCRF as a preexisting condition and medical history. Any clinically relevant finding from vital signs and ECGs that occurs after the first dosing of study drug and results in a diagnosis should be recorded as an AE in eCRF. Information on CV risk factors will be collected on an eCRF at Visit 3 (baseline). In addition to monitoring of vital signs (PR, SBP, DBP) and 12 lead electrocardiograms (ECGs) throughout the study, data on any new CV event will be prospectively collected using a CV event eCRF. CV events will be analyzed using preferred investigator reported terms and abnormal ECG result.~~

~~Deaths will be monitored throughout the study. Relevant data from patients who experienced death will be entered into a specifically designed eCRF page by study site.~~

9.4.1. Electrocardiograms

After enrollment, if a clinically significant finding is identified from the additional ECGs conducted at the discretion of the investigator (including but not limited to changes in QT/QTc interval from baseline), the investigator will determine if the patient can continue on study drug.

9.4.2. Vital Signs Sitting BP and heart rate (PHR) will be measured using standardized equipment provided by the Sponsor according to the Schedule of Activities (Section 2). Vital sign measurements should be taken before obtaining an ECG tracing and before collection of blood samples for laboratory testing, at visits where required (see Schedule of Activities Section 2). The participant should be allowed to sit quietly for 5 minutes before vital sign measurements. An appropriately sized cuff (cuff bladder encircling at least 80% of the arm) should be used to ensure the accuracy of BP measurements. The arm used for the BP measurement should be supported at heart level. At Visit 1 (screening), to determine which arm should be used to collect BP and PHR throughout the study. BP and PHR will be measured once in each arm and the arm that had the higher BP should be used to collect all 2 measurements of both BP and PHR at all study visits. For each parameter (HPR, SBP/diastolic blood pressure [DBP]), 2 measurements will be taken using the same arm; the recordings should be taken at least 1 minute apart. Each measurement of sitting HPR and BP is to be recorded in the eCRF. Any AE related to changes in BP and HPR should be reported.

9.4.5.1.3. Additional hepatic data collection (hepatic safety CRF) in study participants who have abnormal liver tests during the study Hepatic Safety Data Collection

Additional hepatic safety data collection in hepatic safety case report forms (CRF) should be performed in study participants who meet 1 or more of the following 5 conditions:

~~Additional safety data should be collected via the eCRF if 1 or more of the following conditions occur:~~

1. Elevation of serum ALT to ≥ 5 x ULN on 2 or more consecutive blood tests (if baseline ALT < 1.5 x ULN)
 - In participants with baseline ALT ≥ 1.5 x ULN, the threshold is ALT ≥ 3 x baseline on 2 or more consecutive tests
2. Elevated TBL to ≥ 2 x ULN (if baseline TBL < 1.5 x ULN) (except for cases of known Gilbert's syndrome)
 - In participants with baseline TBL ≥ 1.5 x ULN, the threshold should be TBL > 2 x baseline
3. Elevation of serum ALP to ≥ 2 x ULN on 2 or more consecutive blood tests (if baseline ALP < 1.5 x ULN)

- In participants with baseline ALP $\geq 1.5 \times$ ULN, the threshold is ALP $\geq 2 \times$ baseline on 2 or more consecutive blood tests

4. Hepatic event considered to be an SAE

5. Discontinuation of study drug due to a hepatic even

1. ~~Elevation of serum ALT to $\geq 5 \times$ ULN on 2 or more consecutive blood tests if baseline ALT $< 1.5 \times$ ULN; In participants with baseline ALT $\geq 1.5 \times$ ULN, the threshold is ALT $\geq 3 \times$ baseline on 2 or more consecutive tests;~~
2. ~~Elevated TBL to $\geq 2 \times$ ULN if baseline TBL $< 1.5 \times$ ULN (except for cases of known Gilbert's syndrome); In participants with baseline TBL $\geq 1.5 \times$ ULN, the threshold should be TBL $\geq 2 \times$ baseline;~~
3. ~~Elevation of serum ALP to $\geq 2 \times$ ULN on 2 or more consecutive blood tests if baseline ALP $< 1.5 \times$ ULN; In participants with baseline ALP $\geq 1.5 \times$ ULN, the threshold is ALP $\geq 2 \times$ baseline on 2 or more consecutive blood tests;~~
4. Hepatic event considered to be a SAE;
5. Discontinuation of study drug due to a hepatic event.

Note: the interval between the two consecutive blood tests should be at least 2 days.

10.2. Populations for Analyses <<GBDI protocol section 12.2.1.1>>

Table GBGO.7. Populations for Analyses

Population	Description
Per-Protocol (PP)	All patients in ITT and who also meet the following criteria: 
 • Have no protocol deviations expected to impact the primary endpoint for HbA1c (see below); • Complete the treatment period (28 week [Visit 17]) for primary endpoint (that is, do not discontinue from the study drug early); • At least 75% compliant with study drug for at least 75% of the visits.

10.3.1. General Statistical Considerations

Unless otherwise specified, listings will include all randomized patients. Both efficacy and safety analyses will be conducted using the intention to treat (ITT) population. Unless otherwise specified, efficacy data from patients who started rescue therapy or discontinued study treatment prematurely and remain in the study will be censored from the point of initiating rescue treatment or premature discontinuation onwards. Selected analyses will also be conducted using the PP and Completers populations. The PP and Completers populations are subsets of the ITT population.

Two analysis models will be used for the primary and key secondary continuous efficacy measures. The primary analysis will be analyzed with mixed-model repeated measures (MMRM) analysis using restricted maximum likelihood (REML) (Section 10.3.3.1).

The secondary analysis for the primary and key secondary continuous endpoints will be analysis of covariance (ANCOVA) (Section 10.3.3.1 and 10.3.3.2). Missing endpoints will be imputed with the last (postbaseline) observation carried forward (LOCF). The proportion of patients

achieving the target HbA1c of <7.0% will be analyzed using a longitudinal logistic regression with repeated measurements (Section 10.3.3.2).

10.3.3.1. Primary Analyses

The primary outcome is the difference in HbA1c change from baseline between treatment groups based on the ITT population at the planned end of the treatment period of 28 weeks. The ~~primary~~-analysis model will be a MMRM for HbA1c change from baseline to 28 weeks (Visit 17) in the ITT population with treatment, OAM use, visit and treatment-by-visit as fixed effects, baseline HbA1c as a covariate, and patient as a random effect.

The ~~primary~~-analysis model, MMRM, will be repeated using the PP and Completers populations. If the conclusion differs from that of the ITT population, the data and analyses will be further investigated.

~~The secondary analysis model will be an ANCOVA for HbA1c change from baseline to endpoint, with missing endpoints imputed with the LOCF using post baseline data only.~~

10.3.3.2. Secondary Analyses

The key secondary continuous efficacy measures (change from baseline in body weight and FBG) will be analyzed using ~~both models, the MMRM and the ANCOVA with LOCF models.~~ The MMRM model will include independent variables of treatment, OAM usage (metformin alone, acarbose alone, metformin and acarbose), ~~baseline screening~~ HbA1c stratum ($\leq 8.5\%$ vs. $\geq 8.5\%$), visit, and treatment-by-visit as fixed effects and baseline dependent variable as covariates. ~~The ANCOVA model will include independent variables of treatment, OAM usage (metformin alone, acarbose alone, metformin and acarbose), screening HbA1c stratum ($\leq 8.5\%$ vs. $> 8.5\%$) as fixed effects and baseline dependent variable as covariates.~~

10.3.3.3. Tertiary/Exploratory Analyses

The other objectives include triple endpoint (HbA1c <7% and no weight gain [$<0.1\text{ kg}$] at 28 weeks, and no documented symptomatic hypoglycemia [BG $\leq 3.9\text{ mmol/L}$] during the maintenance period); double endpoint (HbA1c <7% at 28 weeks and no documented symptomatic hypoglycemia [BG $\leq 3.9\text{ mmol/L}$] during the maintenance period); Proportion of patients achieving HbA1c target <7.0% and without weight gain ($<0.1\text{ kg}$) at 28 weeks.

Furthermore, we will conduct some additional efficacy analysis without censoring the data after rescue therapy or premature treatment discontinuation (whichever occurs first). Missing endpoints will be imputed by jumping to the reference method. Measurements include actual HbA1c, body weight and FSG and frequency counts and percentage of patients achieving the HbA1c target of <7.0% and changes in these measures from baseline. We will analyze HbA1c, body weight and FSG by ANCOVA. Percentages of patients achieving the target of HbA1c <7.0% will be analyzed using longitudinal logistic regression with repeated measurements.

10.3.4. Safety Analyses

The safety analysis will include analysis of AEs, SAEs, hypoglycemic and hyperglycemic episodes, vital signs, electrocardiogram and laboratory analyses. Unless otherwise specified, the ITT population will be used for analyses of safety measures.

10.3.4.3. Hypoglycemic Episodes

Hypoglycemic episodes will be analyzed using 2 hypoglycemic thresholds: Level 1 (glucose alert level, <3.9 mmol/L [3.9 mmol/L 70 mg/dL] and >3.0 mmol/L [54 mg/dL]) and Level 2 (clinically significant hypoglycemia level, <3.0 mmol/L [3.0 mmol/L 54 mg/dL]). Other categories, including the categories above defined with different glucose thresholds, may also be included in these analyses when deemed appropriate.

The incidence of hypoglycemic episodes will be summarized by frequencies and proportion for each treatment group, by visit as well as overall. Treatment differences in the incidence of hypoglycemic episodes will be assessed using Fisher's exact tests or Chi-square test. Treatment differences in rates of hypoglycemic episodes (episodes/patient/30 days; episodes/patient/year) will be analyzed using a generalized linear mixed-effects model assuming negative binomial distribution. The model will include treatment, OAM usage (metformin alone, acarbose alone, metformin and acarbose), baselinescreening HbA1c stratum ($\leq 8.5\%$ vs. $\geq 8.5\%$), visit, treatment-by-visit interaction, and baseline hypoglycemia rate. The logarithm of days between visits will be included as an offset to account for possible unequal duration between visits and between patients.

Appendix 1. Abbreviations and Definitions

ADA	American Diabetes Association
adjudication committee	An external committee whose purpose is to evaluate study data and decide whether a study endpoint or other criterion has been met.
CEC	Clinical Endpoint Committee
CK	creatine kinase
D.Bil	direct bilirubin
DMC	Data Monitoring Committee
EASD	European Association for the Study of Diabetes
EQ-5D-5L	EuroQol 5-dimension questionnaire
FDAFBG	fasting blood glucose Food and Drug Administration
FBG FDA	fasting blood glucose Food and Drug Administration
FSH	follicle-stimulating hormone
GAD	glutamic acid decarboxylase
HR	heart rate
ICA	islet cell antibodies

LOCF	last observation carried forward
MAR	missing at random
MDDAB	Medication Delivery Device Assessment Battery
MEN	multiple endocrine neoplasia
MNAR	missing not at random
NAFLD	nonalcoholic fatty liver disease
NOAEL	no-observed-adverse-effect level
NPH	neutral protamine Hagedorn
PMM	pattern mixture model
QTcF	QT corrected for heart rate using Fridericia's formula
SDPSUP	single-dose-use pen
SmPC	Summary of Product Characteristics
T2D	type 2 diabetes mellitus
USPI	United States Prescribing Information Package Insert

Appendix 2. Clinical Laboratory Tests

Clinical Laboratory Tests^{a,c}

Calcitonin^e

Pancreas (Exocrine)^e

^c Additional blood samples may be collected based on the investigator's judgment.

^g This value will be calculated. If triglycerides >400 ng/mLmg/dL, then direct LDL will be assayed.

Appendix 4. Liver Safety: Suggested Actions and Follow-Up Assessments

Hepatic Monitoring Tests for Treatment-Emergent Abnormality

Hepatic Evaluation Testing – Refer to protocol Hepatic Safety Monitoring Section 9.4.5.1 for guidance on appropriate test selection.

- For testing selected, analysis is required to be completed by the Lilly designated central laboratory except for those testings that are denoted as local below.
- Local testing may be performed in addition to central testing when required for immediate patient management.
- Results will be reported if a validated test or calculation is available.

Hematology

Hemoglobin

Hematocrit

Erythrocytes (RBCs - Red Blood Cells)

Leukocytes (WBCs - White Blood Cells)

Differential:

Neutrophils, segmented

Lymphocytes

Monocytes

Basophils

Eosinophils

Platelets

Cell morphology (RBC and WBC)

Coagulation

Prothrombin Time, international normalized ratio (PT-INR)

Serology

Hepatitis A Virus (HAV) Testing:

HAV Total Antibody

HAV IgM Antibody

Hepatitis B Virus (HBV) Testing:

Hepatitis B surface antigen (HBsAg)

Hepatitis B surface antibody (Anti-HBs)

Hepatitis B core total antibody (Anti-HBc)

Hepatitis B core IgM antibody

Clinical Chemistry

Total bilirubin

Direct bilirubin

Alkaline phosphatase (ALP)

Alanine aminotransferase (ALT)

Aspartate aminotransferase (AST)

Gamma-glutamyl transferase (GGT)

Creatine kinase (CK)

Other Chemistry

Acetaminophen

Acetaminophen Protein Adducts^c

Alkaline Phosphatase Isoenzymes^c

Ceruloplasmin

Copper^c

Ethyl Alcohol (EtOH)

Haptoglobin

Immunoglobulin IgA (Quantitative)

Immunoglobulin IgG (Quantitative)

Immunoglobulin IgM (Quantitative)

Phosphatidylethanol (PEth) ^c

Urine Chemistry

Drug Screen

Ethyl glucuronide (EtG) ^c

Other Serology

Anti-nuclear antibody (ANA)

Hepatitis B core IgG antibody	Anti-smooth muscle antibody (ASMA) ^a
HBV DNA ^d	Anti-actin antibody ^{c, b}
Hepatitis C Virus (HCV) Testing:	Epstein-Barr Virus (EBV) Testing:
HCV antibody	EBV antibody
HCV RNA ^d	EBV DNA ^d
Hepatitis D Virus (HDV) Testing:	Cytomegalovirus (CMV) Testing:
HDV antibody	CMV antibody
Hepatitis E Virus (HEV) Testing:	CMV DNA ^d
HEV IgG antibody	Herpes Simplex Virus (HSV) Testing:
HEV IgM antibody	HSV (Type 1 and 2) antibody
HEV RNA ^d	HSV (Type 1 and 2) DNA ^{c, d}
Microbiology ^c	Liver Kidney Microsomal Type 1 (LKM-1) Antibody
Culture:	
Blood	
Urine	

^a Not required if anti-actin antibody is tested.

^b Not required if anti-smooth muscle antibody (ASMA) is tested.

^c Assayed ONLY by investigator-designated local laboratory if available; no central testing available.

^d Reflex/confirmation dependent on regulatory requirements, testing availability, or both.

Hepatic Monitoring Tests

Hepatic Hematology*	Haptoglobin*
Hemoglobin	
Hematocrit	Hepatic Coagulation*
RBC	Prothrombin Time
WBC	Prothrombin Time, INR
Neutrophils, segmented	
Lymphocytes	Hepatic Serologies^{a,b}
Monoocytes	Hepatitis A antibody, total
Eosinophils	Hepatitis A antibody, IgM
Basophils	Hepatitis B surface antigen
Platelets	Hepatitis B surface antibody
	Hepatitis B Core antibody
Hepatic Chemistry*	Hepatitis C antibody
Total bilirubin	Hepatitis E antibody, IgG
Direct bilirubin	Hepatitis E antibody, IgM
Alkaline phosphatase	
ALT	Anti-nuclear antibody*
AST	
GGT	Alkaline Phosphatase Isoenzymes*
CPK	Anti-smooth muscle antibody (or anti-actin antibody)*

Abbreviations: ALT = alanine aminotransferase; AST = aspartate aminotransferase; CPK = creatinine phosphokinase; GGT = gamma glutamyl transferase; Ig = immunoglobulin; INR = international normalised ratio; RBC = red blood cells; WBC = white blood cells.

^a—Assayed by Lilly designated or local laboratory.

^b—Reflex/confirmation dependent on regulatory requirements and/or testing availability.

- Removed analyses for hypoglycemia events with post-rescue or early-discontinuation data.
- Removed interaction term and covariate in negative binomial model for hypoglycemia events.
- Modified shift tables for selected analytes.
- Added baseline insulin dose in subgroup analysis.
- Updated number of patients required for subgroup analysis.
- Added Chinses EQ-5D-5L score in addition to UK score.

4. Study Objectives

Table 4.1 Table 4.1 Objectives and Endpoints presents the objectives and endpoints of the study.

Table 4.1 Objectives and Endpoints

Objectives	Endpoints

Primary
 
 To show the superiority of the addition of dulaglutide 1.5 mg QW compared to the addition of once weekly placebo to titrated insulin glargine, with metformin and/or acarbose, on change from baseline in HbA1c after 28 weeks of treatment in adult Chinese patients with T2D. 	
 The change in HbA1c from baseline to Week 28.

Key Secondary (controlled for Type I error)
 
Efficacy:
 
 To compare the addition of dulaglutide 1.5 mg QW with the addition of placebo QW to titrated basal insulin glargine for other parameters of glucose control and body weight change after 28 weeks of treatment in patients with T2D. 	
 Proportion of patients achieving HbA1c target of <7.0%. Change from baseline in body weight. Change from baseline in FSG (central lab).

Additional Secondary
 
Efficacy:
 
 To compare the addition of dulaglutide 1.5 mg QW with the addition of placebo QW to titrated basal insulin glargine for the following parameters after 28 weeks of treatment in patients with T2D. 	
 Proportion of patients achieving HbA1c target of ≤6.5%. Proportion of patients achieving HbA1c target of <7.0% and with no weight gain (<0.1 kg) at 28 weeks, and without documented symptomatic hypoglycemia (BG <3.0 mmol/L) during the maintenance period (Weeks 12-28). Proportion of patients achieving HbA1c target of <7.0% at 28 weeks, and without documented symptomatic hypoglycemia (BG <3.0 mmol/L) during the maintenance period (Weeks 12-28). Proportion of patients achieving HbA1c target of <7.0%, and without weight gain (<0.1 kg) at 28 weeks. Changes from baseline in BG from daily SMBG profiles. Changes from baseline in daily mean insulin glargine doses.


Safety:
 
 • To compare the addition of dulaglutide 1.5 mg QW with the addition of placebo QW to titrated basal insulin glargine for selected safety parameters through 32 weeks in patients with T2D (unless noted otherwise). 	
 • Incidence of TEAEs, SAEs and discontinuation of study drug due to AEs. • Change from baseline in electrocardiograms, laboratory and vital sign measurements. • Incidence of AESI. • The incidence of deaths and nonfatal CV events. • Occurrence of hypoglycemic episodes. • Incidence of patients initiating rescue therapies due to severe, persistent hyperglycemia. • Incidence of adjudicated and confirmed pancreatitis. • Incidence of thyroid neoplasm. • Incidence of allergic and hypersensitivity AEs.

Exploratory
 
Efficacy:
 
 • To compare the addition of dulaglutide 1.5 mg QW with the addition of placebo QW to titrated basal insulin glargine for exploratory efficacy parameters after 28 weeks of treatment in patients with T2D. 	
 • Frequency of insulin dose adjustments through 28 weeks. • Number of insulin dose assessments per TTT algorithm and compliance with the TTT algorithm at Week 6, 8, and 12. • Proportion of patients achieving HbA1c target of <7.0%, and without weight gain (<0.1 kg) at Week 28, and without documented symptomatic hypoglycemia (BG <3.9 mmol/L) during the maintenance period (Weeks 12-28). • Proportion of patients achieving HbA1c target <7.0% and without weight gain (<0.1 kg) at Week 28; • Proportion of patients achieving HbA1c target of <7.0% at Week 28, and without documented symptomatic hypoglycemia (BG <3.9 mmol/L) during the maintenance period.

Safety:
 
 • To compare the addition of dulaglutide 1.5 mg QW with the addition of placebo QW to titrated basal insulin glargine for exploratory safety parameters through 32 weeks in patients with T2D. 
Health Outcome/Quality of Life Measures:
 
 • To compare the addition of dulaglutide 1.5 mg QW with the addition of placebo QW to titrated basal insulin glargine for the following HO/QoL parameters in patients with T2D. 	
 • Assessments of time to onset and duration of diarrhea, nausea, abdominal distension and vomiting in dulaglutide-treated patients. 
 • Changes from baseline in patient-reported health status as measured by the EuroQol 5-dimension 5-level questionnaire (EQ-5D-5L) at 12 and 28. • Changes from baseline in patient-reported weight-related self-perception as measured by the Impact of Weight on Self-Perception Scale (IW-SP) at 12 and 28.

- Assessments of patient perceptions regarding use and specific features of the delivery devices using the following modules of the Medication Delivery Device Assessment Battery (MDDAB):
 - Module 1: Single-Use Pen (SUP) Ease of Use Module (Week 6 and 28).
 - Module 2: SUP Device Features Module (Week 6 and 28).
 - Module 3a: SUP Experience Module (Week 6).
 - Module 3b: SUP Experience Module (Week 28).
 - Module 4: Glargine Delivery Device Experience Module (Week 28).

Abbreviations: CV = Cardiovascular; EQ-5D-5L = EuroQol 5-dimension 5-level questionnaire; FSG = fasting serum glucose; HbA1c = hemoglobin A1c; IW-SP = Impact of Weight on Self-Perception Scale; MDDAB = Medication Delivery Device Assessment Battery; BG = blood glucose; SMBG = self-monitored blood glucose; SUP = Single-Use Pen; T2D = type 2 diabetes; TTT = treat-to-target.

5. A Priori Statistical Methods

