 2. Injection site erosion
 3. Injection site erythema

4. Injection site hypersensitivity
5. Injection site induration
6. Injection site pruritus
7. Injection site exfoliation
8. Injection site vasculitis
9. Injection site photosensitivity reaction
10. Injection site rash
11. Injection site urticaria
12. Injection site hypertrophy
13. Injection site inflammation
14. Injection site irritation
15. Injection site oedema
16. Injection site warmth

For hepatic safety, apply the Drug related hepatic disorders - comprehensive search SMQ (20000006).

All AEs and treatment-emergent adverse events (TEAEs), defined as an event that first occurs or worsens (increases in severity) on or after first dose will be listed by patient and visit using MedDRA PT and SOC. Information on treatment, preferred term, reported term, severity, seriousness, and relationship to study drug will be reported. Listings of patients with study and study drug discontinuation due to AEs or death will be produced.

Summary statistics will be provided for TEAEs, SAEs, and study and study drug discontinuation due to AEs or death during the treatment period and through safety follow-up. Counts and proportions of patients experiencing AEs will be reported for each treatment group, and Fisher's exact tests will be used to compare the treatment groups.

Listings and summary statistics will also be provided for adverse event of special interest (AESI) including deaths, hypoglycemia, severe, persistent hyperglycemia, nonfatal CV events, adjudicated and confirmed pancreatitis, thyroid neoplasm, allergic and hypersensitivity reactions.

Since gastrointestinal (GI) AEs, like diarrhea, nausea, abdominal distension and vomiting, are among the most common events reported in patients treated with dulaglutide, summaries and analyses for onset, duration, and severity of diarrhea, nausea, abdominal distension and vomiting will be provided. The duration of an adverse event was calculated as adverse event end date minus the adverse event start date plus 1 day and was reported in terms of median number of days. Time to onset of an adverse event was analyzed by day, from the first dose date of the study drug to the occurrence of the adverse event.

The following PTs will be used to identify GIAEs:

1. Specific diarrhea symptoms include the following PTs
 - a. Diarrhea (10012735)
 - b. Fecal volume increased (10049939)

- c. Frequent bowel movements (10017367)
- 2. Specific nausea symptoms include the following PTs

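### The exploratory GI safety objective compares dulaglutide with placebo, but its only endpoint is confined to dulaglutide patients and no between-arm analysis of GI onset or duration is specified

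*SAP*

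**What the plan says.** The exploratory safety row of SAP Table 4.1 (Section 4), which covers follow-up to Week 32, is comparative: "To compare the addition of dulaglutide 1.5 mg QW with the addition of placebo QW to titrated basal insulin glargine for exploratory safety parameters". The only endpoint in that row is "Assessments of time to onset and duration of diarrhea, nausea, abdominal distension and vomiting in dulaglutide-treated patients". Protocol Table GBGO.2 (Section 4) carries the same objective and the same endpoint.

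The methods text is in SAP 5.11.1. It promises that "summaries and analyses for onset, duration, and severity of diarrhea, nausea, abdominal distension and vomiting will be provided", without naming arms. Onset is counted in days "from the first dose date of the study drug to the occurrence of the adverse event". On duration it says: "The duration of an adverse event was calculated as adverse event end date minus the adverse event start date plus 1 day", reported as a median number of days. For adverse events in general the same section says: "Counts and proportions of patients experiencing AEs will be reported for each treatment group", with Fisher's exact test between groups. Protocol 10.3.4.2 contains no separate analysis of GI onset or duration.

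Two other places bear on the point. SAP 5.11 makes the ITT population the default for safety analyses unless something else is specified, and SAP Table 5.1 defines ITT to include both arms. SAP 5.11.3 analyses time to rescue with a Cox model and a Kaplan-Meier plot showing both treatments.

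**The concern.** An objective that compares two arms is not met by an endpoint defined in one of them. All patients continue metformin and/or acarbose with titrated glargine, so only the randomised placebo arm shows when GI symptoms start, and how long they last, on background treatment alone. The mismatch is in the current text of both documents, and the methods section does not settle it. One programmer could follow the table and produce a dulaglutide-only display. Another could follow the ITT default and produce two columns.

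The second part is the onset measure. A patient who never has the symptom has no date of occurrence, and the SAP does not say how such a patient enters the analysis. If onset is summarised only among patients with an event, the summary conditions on something that happens after randomisation, and it need not reflect the difference in risk over time between the arms.

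**Working it through.** **The plan's own figures.** The documents give no figure for the GI endpoint. The group size used below does reproduce:
- Per arm, n = 2(1.960 + 1.282)² × 1.2² / 0.5² ≈ 121, or 122 with the t correction (t-based solution 122.01, which rounds up to 123).
- Power at 123 per arm is 0.904 (0.902 by t-test).
- 123 / 0.85 = 144.7, so 145 per arm and 290 in total, as stated in SAP 5.1.

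The GI point does not depend on this calculation.

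**The texts side by side.**
- Objective, both tables: dulaglutide against placebo.
- Endpoint, both tables: dulaglutide patients only.
- Methods, SAP 5.11.1: arms not named. No test, model or censoring rule for GI onset, and no rule for events that are ongoing or recur.
- Time to rescue, SAP 5.11.3: Cox model and Kaplan-Meier, both arms.

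The tables therefore conflict within one row, and the methods text neither repeats nor resolves the conflict.

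**Could an onset summary among patients with events hide a difference?** This is an illustration. The incidences are assumptions and are not in the documents. Follow-up is T = 224 days (32 weeks), the hazard is constant, and there are 145 patients per arm. For incidence p:
- hazard h = −ln(1 − p) / T
- median onset among patients with an event = −ln(1 − p/2) / h
- expected events = 145p

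Worked case, 15% against 5%:
- Dulaglutide: h = 0.1625 / 224. Median = 0.0780 × 224 / 0.1625 = 107.5 days.
- Placebo: h = 0.0513 / 224. Median = 0.0253 × 224 / 0.0513 = 110.6 days.
- Hazard ratio = 0.1625 / 0.0513 = 3.17.

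| Assumed incidence, dulaglutide vs placebo | Hazard ratio | Median onset among patients with events (days) | Difference (days) | Expected events |
|---|---|---|---|---|
| 10% vs 5% | 2.05 | 109.1 vs 110.6 | 1.5 | 14.5 vs 7.2 |
| 15% vs 5% | 3.17 | 107.5 vs 110.6 | 3.1 | 21.8 vs 7.2 |
| 20% vs 5% | 4.35 | 105.8 vs 110.6 | 4.8 | 29.0 vs 7.2 |
| 30% vs 10% | 3.39 | 102.1 vs 109.1 | 7.0 | 43.5 vs 14.5 |

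**Could the planned data support a comparison?** For a two-arm comparison of time to first event with censoring, the Schoenfeld approximation with D expected events, 1:1 allocation and two-sided 0.05 gives power Φ(√(D/4) × ln HR − 1.96). For 15% vs 5%, D = 29: √7.25 × ln 3.17 − 1.96 ≈ 1.14, so power is about 0.87. The four cases give about 0.39, 0.87, 0.99 and over 0.99. At all but the lowest assumed rates, the data already planned would be informative.

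**The case against.** The strongest reply is that the methods section governs. SAP 5.11.1 plans the GI summaries with no arm restriction, and the safety default is ITT, so placebo patients are included unless the table label is taken to override that. Whether dulaglutide produces more GI events than placebo is tested directly through adverse event incidence with Fisher's exact test. This stands, and it rules out three stronger readings that a reader might infer.

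- *That the objective cannot be answered.* GI events are recorded in both arms, incidence is compared, and SAP 5.2 allows additional exploratory analyses. What is missing is a specified between-arm analysis of onset and duration.
- *That half of the randomised patients, 145 of 290, fall outside the analysis.* This holds only if the table wording overrides SAP 5.11.1 and the ITT default. The documents do not say which prevails.
- *That the SAP reports a median onset among patients with events only.* The SAP attaches the median to duration. For onset it gives only start and end points. That event-free patients drop out is inferred from the definition and the absence of a censoring rule. The SAP does not state it.

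It can also be said that, for patients who do get nausea, when it starts and how long it lasts is a fair descriptive question, and that duration exists only for patients with events under any method. Both are true. They support describing duration rather than testing it. They do not reconcile a comparative objective with a one-arm endpoint. Finally, the endpoint is exploratory and outside the type I error scheme in SAP 5.3, which limits the weight of the point.

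**Conclusion.** The point holds in a limited form. The objective and its only endpoint contradict each other in both documents, and the SAP specifies no between-arm analysis of GI onset or duration and no treatment of event-free patients in the onset measure. The contradiction rests on the text alone and needs no assumption.

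Its numerical size cannot be taken from the documents. Under the assumed rates above, a two- to fourfold difference in hazard shows up as 1.5 to 7 days in median onset among patients with events. That depends on constant hazards. With another hazard shape the medians could separate further, so the illustration shows only that they need not reveal the difference. Importance is low: no primary, key secondary or adverse event incidence conclusion changes.

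**What to change.** 1. In Protocol Table GBGO.2 and SAP Table 4.1, delete the closing words that confine the endpoint to the dulaglutide arm.
2. In SAP 5.11.1, state that onset, duration and severity of the four GI symptoms are summarised for both arms.
3. Define onset as time from first dose to first event of each symptom. Present it by arm with Kaplan-Meier curves over all ITT patients, censoring event-free patients at last contact.
4. Describe duration by arm among patients with events, and say how ongoing and recurrent events are counted. Because these patients are selected after randomisation, present this as description.

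If the sponsor wants only a description of dulaglutide patients, the alternative is to reword the objective as descriptive. Either way the two cells must agree.

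The cost is one more exploratory display, a few sentences in the SAP and a small wording change to the protocol table. No new data are needed.
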